4.5.2 Data Collection and Follow-up for Withdrawn Subjects

Withdrawn subjects will be removed from the analysis and no follow up will be undertaken.

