3.3 Primary Safety Endpoints

As stated previously in section 1.9, we will use 4 mCi±10% Cu-64-TP3805 dose given with FDA approval to fifteen of the nineteen BC patients. The peptide quality (20 µg) will also be kept unchanged.

There was no toxicity in this entire study of the nineteen subjects except three subjects sensed flushing which resolved within minutes without any medication. It is reasonable therefore to anticipate that in this PC study too, there will be no adverse events (AE) due to dose administered. Nevertheless, a physician (either [name] or [name]) will be available during and after the injection. An up to date first aid box will be available. The Research Coordinator will call each subject 24 hrs later and make note of any AE patients may have experienced.

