4.5 Early Withdrawal of Subjects

4.5.1 When and How to Withdraw Subjects

Patients who withdraw consent or who do not complete the investigational imaging or who do not have radical prostatectomy will be withdrawn from study and will not be included in the analysis.

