5.2 Treatment Regimen

A protocol assistant from the Urology Department will assist with accrual and enrollment, and a clinical coordinator from the Radiology Department will guide the patient through the imaging procedure. IRB approved informed consent

will be obtained by one of the investigators. The patients will be asked to read the IRB-approved consent form and encouraged to ask any questions they deem necessary. Four ±10% mCi of Cu-64-TP3805, prepared as described here in will be injected through an indwelling intravenous line and the lines will be flushed with 5 ml sterile 0.9% saline. Patient vital signs (heart rate, respiratory rate, blood pressure) will be monitored before administration, at 15 minute post injection and then at the end of the scan. Patients will be scanned at 90 minutes with whole body PET/CT. Imaging time will be approximately one hour. Patients will be contacted over the phone 24 hours later and asked for any unlikely adverse events. Any AE shall be recorded and notified immediately to IRB, FDA and to CCRRC.

Whole body PET/CT imaging will be acquired by a trained and experienced technologist at Jefferson Center City Imaging facility located within the TJU campus. Images will be read either by [name] or [name]. Data will be recorded. Care will be taken of patient privacy.

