5.3 Risks

Based on the previous nineteen recipients of Cu-64-TP3805, we do not anticipate any adverse events after the i.v. administration of peptide analog, the patients will remain in the clinic for at least two hours and observed either by the technologist or by the research coordinator. [name] and [name] will be available should their expertise be required. A first aid box equipped appropriately will be at hand all the time.

Patient vital signs (heart rate, respiratory rate, blood pressure) will be monitored before administration, at 15 minute post injection and then at the end of the scan. Patients will be scanned at 90 minutes with whole body PET/CT The nursing staff will also watch for any flushing or redness. Each reading will be recorded.

Twenty-four hours later, we will telephone each patient to ask for any adverse events the patient may experience. These will be recorded.

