All unresolved adverse events should be followed by the investigator until the events are resolved, the subject is lost to follow-up, or the adverse event is otherwise explained. At the last scheduled visit, the investigator should instruct each subject to report any subsequent event(s) that the subject, or the subject's personal physician, believes might reasonably be related to participation in this study. The investigator should notify the study sponsor of any death or adverse event occurring at any time after a subject has discontinued or terminated study participation that may reasonably be related to this study. The sponsor should also be notified if the investigator should become aware of the development of cancer or of a congenital anomaly in a subsequently conceived offspring of a subject that has participated in this study.

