8.2 Recording of Adverse Events

At each contact with the subject, the investigator must seek information on adverse events by specific questioning and, as appropriate, by examination. Information on all adverse events should be recorded immediately in the source document, and also in the appropriate adverse event module of the case report form (CRF). All clearly related signs, symptoms, and abnormal diagnostic procedures results should be recorded in the source document, though should be grouped under one diagnosis.

All adverse events occurring during the study period must be recorded

The clinical course of each event should be followed until resolution, stabilization, or until it has been determined that the study treatment or participation is not the cause. Serious adverse events that are still ongoing at the end of the study period must be followed up to determine the final outcome. Any serious adverse event that occurs after the study period and is considered to be possibly related to the study treatment or study participation should be recorded and reported immediately.

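### The withdrawal rules in 4.5 remove men who have no prostatectomy although the reference is biopsy, and end follow-up with no exception for injected men

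*Combined protocol and SAP*

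**What the plan says.** Section 4.5.1 lists three grounds for withdrawal: withdrawn consent, men "who do not complete the investigational imaging", and men "who do not have radical prostatectomy will be withdrawn from study and will not be included in the analysis". Section 4.5.2 then states: "Withdrawn subjects will be removed from the analysis and no follow up will be undertaken". Neither section separates men already injected from men not yet injected, or the accuracy analysis from a safety summary.

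Other sections say different things:

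- **Reference standard.** Section 3.2 compares PET with histology of biopsy specimens. Section 7.3 defines one analysis population, men who complete imaging and undergo biopsy. The visit chart in 15.1 ends participation once biopsy pathology is received and contains no prostatectomy.
- **24-hour call.** Section 3.3: "The Research Coordinator will call each subject 24 hrs later and make note of any AE patients may have experienced". Section 5.3: "Twenty-four hours later, we will telephone each patient to ask for any adverse events the patient may experience". Section 5.2: "Patients will be contacted over the phone 24 hours later and asked for any unlikely adverse events".
- **Open events.** Section 8.1: "All unresolved adverse events should be followed by the investigator until the events are resolved", or until the subject is lost to follow-up or the event is otherwise explained. Section 8.2: "Serious adverse events that are still ongoing at the end of the study period must be followed up to determine the final outcome".
- **After discontinuation.** The post-study part of 8.1 asks the investigator to notify the sponsor of deaths and events that may be related, even after a subject has left the study.
- **Replacement.** Section 7.4 replaces only men who consented but were not dosed.

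**The concern.** Injected men can fall under 4.5. The scan starts 90 minutes after injection and lasts about an hour (5.2), and biopsy follows one to three weeks later (6.1, 15.1).

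Two consequences follow. For accuracy, the prostatectomy trigger would discard men who did everything the study asks of them. The loss would fall mainly on men whose biopsy shows no cancer, whom the plan needs in order to show that PET can identify absence of cancer. For safety, staff dealing with an injected man who stops early meet one section that ends follow-up and others that require it. Section 3.3 is headed Primary Safety Endpoints, yet the only population in 7.3 is completers, so a safety summary built on that set could leave out men who received the agent.

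**Working it through.** **1. The plan's own precision figure.** Inputs from the sample size text in Section 7: N = 20, expected accuracy 0.80. Wald half-width = 1.96 × √(0.80 × 0.20 / 20) = 0.175. This reproduces the stated ±17.5 points (62.5% to 97.5%).

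**2. The prostatectomy trigger read literally.** Inputs: N = 20 and the plan's 60% cancer figure. Assumption, not in the documents: men without cancer do not have prostatectomy.

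- Expected men without cancer: 20 × (1 − 0.60) = 8. The 2.5th and 97.5th percentiles of Binomial(20, 0.40) are 4 and 12.
- These 8 are a minimum, because men with cancer who have no prostatectomy would also be withdrawn. At most about 12 remain, and 7.4 does not replace the others.
- Wald half-width at 80% accuracy, 1.96 × √(0.16 / n):

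| Men removed | n left | Half-width (points) |
|---|---|---|
| 0 | 20 | 17.5 |
| 4 | 16 | 19.6 |
| 8 | 12 | 22.6 |
| 12 | 8 | 27.7 |

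**3. What the remaining men can estimate.** If essentially all have cancer, the result is sensitivity and not accuracy. With 60% prevalence, accuracy = 0.60 × sensitivity + 0.40 × specificity. An accuracy of 0.80 fits any pair from sensitivity (0.80 − 0.40) / 0.60 = 0.67 with specificity 1, to sensitivity 1 with specificity (0.80 − 0.60) / 0.40 = 0.50. So the same true accuracy of 80% could appear as anything from 67% to 100% in the men left.

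**4. Follow-up, section against section.**

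| Injected man | Section 4.5.2 | Other sections |
|---|---|---|
| Stops before the 24-hour call | No follow-up | Call to every subject (3.3, 5.2, 5.3) |
| Withdrawn with an unresolved event | No follow-up | Followed by the investigator (8.1) |
| Withdrawn with an ongoing serious event | No follow-up | Followed to final outcome (8.2) |
| Has a possibly related event after leaving | No follow-up | Sponsor notified (8.1) |

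**5. Injected non-completers.** Their number is not given. If 1 to 4 of 20 injected men are lost, n is 19 to 16 and the half-width is 18.0 to 19.6 points. For illustration only: flushing occurred in 3 of 19 earlier subjects, 15.8% (exact 95% CI 3.4% to 39.6%). If stopping is unrelated to reacting, a completers-only summary would omit on average 1 × 3/19 = 0.16 flushing events for one non-completer and 3 × 3/19 = 0.47 for three. With no non-completers nothing is omitted.

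**6. Event period (minor).** In 8.1 the period starts with the first study procedure and ends 24 hours after the imaging procedure. The end is unclear for an injected man who is not scanned. The Study Summary gives a 24-hour call without tying it to a completed scan.

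**The case against.** The prostatectomy wording looks like carry-over from the earlier cohort of 25 men scheduled for prostatectomy described in 1.8, and 3.2, 7.3 and 15.1 agree on biopsy. Staff would probably apply biopsy. That is plausible, but 4.5.1 is operative text and fixes who is analysed.

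On follow-up, 4.5.2 can be read as ending study data collection only, with Section 8 governing safety. Section 8 does cover men who have left, and this limits the practical harm. But 4.5.2 is the section written for withdrawn subjects, and it neither refers nor yields to Section 8. Where a man withdraws consent, ending contact may simply respect his decision. That stands, though 9.1 lets data collected before authorization is revoked be used.

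The only specified analysis is diagnostic accuracy, so the word analysis in 4.5 may mean just that, and an unstated safety population is then a gap more than an error. This is fair, and is why that part carries less weight.

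A reader might infer more than the documents support:

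- *That events in withdrawn men would be hidden from oversight.* Reporting to the IRB, Medical Monitor and DSMC (5.2, 8.3.1, 8.3.2, 10.1) is not limited to completers, and Section 13 says all data will be published.
- *That flushing would be missed.* Earlier flushing resolved within minutes, and men are observed on site for at least two hours (5.3).
- *That the prostatectomy trigger shrinks the safety data to about 12 men.* Men who finish the visit chart have already been observed and called, so their safety data exist.
- *That 8.1 leaves the time between injection and scan uncovered.* It does not; only the end of the period depends on imaging.

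**Conclusion.** The point holds and should be fixed.

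The prostatectomy trigger is the most consequential part. Read literally, it removes about 8 of 20 men or more (95% binomial range 4 to 12), leaves a group of about 12 or fewer with essentially no cancer-free men, and widens the half-width from 17.5 to about 22.6 points. This rests on the plan's 60% figure, on the assumption that men without cancer have no prostatectomy, and on the rule being applied as worded.

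The rule against follow-up contradicts 3.3, 5.2, 5.3, 8.1 and 8.2 for injected men. That is a matter of text and needs no numerical assumption. Its practical effect is limited by Section 8.

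The missing safety population creates a risk of omission whose size cannot be stated, because the number of injected non-completers is unknown. The flushing figures only illustrate it. The end of the event period is a minor ambiguity.

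**What to change.** - Reconcile the radical-prostatectomy ground in 4.5.1 with the biopsy reference in 3.2, 7.3 and 15.1.
- Limit removal under 4.5.1 and 4.5.2 to the diagnostic-accuracy analysis.
- State in 7.3 that safety is summarised for all men injected with Cu-64-TP3805, whether or not scan and biopsy are completed.
- Reconcile the follow-up sentence in 4.5.2 with 3.3, 5.2, 5.3, 8.1 and 8.2 for injected men, as far as consent allows.
- Reconcile the end of the event period in 8.1 with the Study Summary for injected men who are not scanned.

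The cost is a few sentences in 4.5, 7.3 and 8.1. No new data are needed, because Sections 3.3, 5 and 8 already call for the observation, the telephone call and the event records.

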5.0 STUDY IMAGING AGENT

5.1 Description

In this investigation, we will use the same preparation, Cu-64-TP3805 that has been prepared and used in nineteen previous human BC subjects with 100% success. Although no preparation will either be compounded or used out of the Jefferson campus, we will use a "kit" that will be ready to be heated following the addition of 440 μL of sterile H2O and then Cu-64 activity. These kits will contain all chemicals in sterile, 10 mL glass vials. Reagents will be added to the vial, snap frozen in dry ice, lyophilized and the vials will be sealed in N2 atmosphere. They will be stored at 4°C and examined for Cu-64 labeling and shelf life stability. Such preparations will be convenient and assure consistency of reagents. Such kits prepared previously in our laboratory were stable for more than two years. We expect similar stability, but will be used only after careful examination of their reproducible and stable preparations, as examined by HPLC. There will be only one patient studied at a time. The syringe containing the Cu-64-TP3805 will be clearly labeled with patient's name. All preparations were sterile. However, sterility will be examined on each dose.

5.2 Treatment Regimen

A protocol assistant from the Urology Department will assist with accrual and enrollment, and a clinical coordinator from the Radiology Department will guide the patient through the imaging procedure. IRB approved informed consent

will be obtained by one of the investigators. The patients will be asked to read the IRB-approved consent form and encouraged to ask any questions they deem necessary. Four ±10% mCi of Cu-64-TP3805, prepared as described here in will be injected through an indwelling intravenous line and the lines will be flushed with 5 ml sterile 0.9% saline. Patient vital signs (heart rate, respiratory rate, blood pressure) will be monitored before administration, at 15 minute post injection and then at the end of the scan. Patients will be scanned at 90 minutes with whole body PET/CT. Imaging time will be approximately one hour. Patients will be contacted over the phone 24 hours later and asked for any unlikely adverse events. Any AE shall be recorded and notified immediately to IRB, FDA and to CCRRC.

Whole body PET/CT imaging will be acquired by a trained and experienced technologist at Jefferson Center City Imaging facility located within the TJU campus. Images will be read either by [name] or [name]. Data will be recorded. Care will be taken of patient privacy.

5.3 Risks

Based on the previous nineteen recipients of Cu-64-TP3805, we do not anticipate any adverse events after the i.v. administration of peptide analog, the patients will remain in the clinic for at least two hours and observed either by the technologist or by the research coordinator. [name] and [name] will be available should their expertise be required. A first aid box equipped appropriately will be at hand all the time.

Patient vital signs (heart rate, respiratory rate, blood pressure) will be monitored before administration, at 15 minute post injection and then at the end of the scan. Patients will be scanned at 90 minutes with whole body PET/CT The nursing staff will also watch for any flushing or redness. Each reading will be recorded.

Twenty-four hours later, we will telephone each patient to ask for any adverse events the patient may experience. These will be recorded.

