Study Duration	3 years
Study Center(s)	Single-center.
Objectives	The objective is to validate the PET imaging results of Cu-64-TP3805, with the histology of the image guided biopsy results. Generally, approximately 60% of the patients with elevated PSA have prostate cancer
Number of Subjects	20
Diagnosis and Main Inclusion Criteria	We will study 20 patients with persistently elevated PSA whom are scheduled for biopsy These patients shall be PET imaged with our Cu-64 peptide probe first and then a week or so later the image guided biopsy shall be performed. The image guided biopsy is the standard of care procedure. The objective is to validate the PET imaging results with the histology of biopsy results. Generally, approximately 60% of the patients with elevated PSA have prostate cancer. We expect 80% accuracy in identifying 20 subjects as having histologically determined cancer/absence of cancer. The 95% confidence interval of this level of accuracy for this sample size is + or – 17.5%. Thus we expect to find an accuracy level between 62.5% to 97.5%. Please note this is a pilot study, not designed to be an efficacy determination trial.
Study Therapy, Dose, Route, Regimen	Cu-64-TP3805, a novel PET imaging molecule, given as a single intravenous injection dose of (4 mCi ±10%).
Duration of administration and follow-up	Single Intravenous administration given over 5 minutes and patients observed for 90 min; follow up, call 24 hrs later.
Reference therapy	N/A

Statistical Methodology	We expect 80% accuracy in identifying 20 subjects as having histologically determined cancer/absence of cancer. The 95% confidence interval of this level of accuracy for this sample size is + or – 17.5%. Thus we expect to find an accuracy level between 62.5% to 97.5%. Please note this is a pilot study, not designed to be an efficacy determination trial.
Schema	Subjects will undergo Cu-64-TP3805 PET Imaging at least one week prior to biopsy. Investigational PET imaging will be analyzed and compared to biopsy pathology to determine efficacy in detection and localization of PC foci. Urine sample will be collected prior to Cu-64 injection and 90 minutes post injection prior to imaging

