Such preparations will be convenient and assure consistency of reagents. Such kits prepared previously in our laboratory were stable for more than two years. We expect similar stability, but will be used only after careful examination of their reproducible and stable preparations, as examined by HPLC. There will be only one patient studied at a time. The syringe containing the Cu-64-TP3805 will be clearly labeled with patient's name. "Cu-64-TP3805" name, the amount of radioactivity, and the time at which the dose was dispensed.

Please note that under this eIND 101550 and with all institutional approvals, the agent was administered to nineteen females with known BC. All malignant lesions including involved lymph nodes were unequivocally delineated (100%). There were no adverse events except three patients sensed flushing which resolved without any medication within a few minutes. Therefore, we will not change this preparation (Cu-64-TP3805). A preprint (J Nucl Med July 2013) of this investigation, reference [79].

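### No vital-sign reading is scheduled between pre-dose and 15 minutes, so the one reaction reported with this agent could come and go without a concurrent heart rate or blood pressure

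*Combined protocol and SAP*

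**What the plan says.** Sections 5.2 (Treatment Regimen) and 5.3 (Risks) give the same schedule: heart rate, respiratory rate and blood pressure "will be monitored before administration, at 15 minute post injection and then at the end of the scan". Section 6.1 adds no time point and refers back to the monitoring already described.

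The Study Summary gives the length of dosing: "Single Intravenous administration given over 5 minutes and patients observed for 90 min". Scanning starts at 90 minutes, and section 5.2 adds: "Imaging time will be approximately one hour".

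On what has been seen with this agent, section 1.8 reports that among nineteen women with breast cancer "three patients sensed flushing which resolved without any medication within a few minutes". Section 3.3 repeats it: "three subjects sensed flushing which resolved within minutes without any medication". Neither says when the flushing began.

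The plan also provides for observation. Section 5.3 keeps subjects in the clinic for at least two hours under the eye of the technologist or coordinator, and says: "The nursing staff will also watch for any flushing or redness". Under section 3.3 a physician "will be available during and after the injection". Section 8.2 says that "the investigator must seek information on adverse events by specific questioning and, as appropriate, by examination", and asks that each event be followed to resolution or stabilisation, or until the study is ruled out as its cause.

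**The concern.** The schedule fits poorly with the one reaction the protocol reports. That reaction is short, and the first reading after dosing comes at 15 minutes. A flush that begins around the injection could be over by then, leaving a normal pre-dose reading, a normal 15-minute reading and nothing in between.

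What is at stake is the content of the safety record. Section 5.2 requires any adverse event to be recorded and notified at once to the IRB, the FDA and the cancer center's review committee. A heart rate and blood pressure taken during the flush would help show whether it is confined to the skin. The question is reasonable for this agent: section 1.4.1 describes TP3805 as an analogue of PACAP27, in the vasoactive intestinal peptide family, and more potent than VIP28. The rabbit toxicology results in section 1.5.1 cover chemistry, blood counts, body weight, cAMP and histology, but give no heart-rate or blood-pressure data.

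**Working it through.** The plan gives no figure of its own on this point, so there is none to reproduce. The check sets the reading times beside the timing of the reported reaction.

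**Inputs from the document**
- Readings: pre-dose, 15 minutes post injection, end of scan (5.2, 5.3).
- Injection: 5 minutes (Study Summary).
- Scan: starts at 90 minutes and lasts about 60 minutes (5.2).
- Reported reaction: flushing in 3 of 19, resolved within a few minutes (1.8, 3.3).

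**Assumptions**
- A few minutes means 2 to 10 minutes.
- Minute 0 is the start of the injection.
- The text does not say whether 15 minutes counts from the start or the end of the injection, so both are shown.

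**Step 1. Times of the readings**
- End of scan: 90 + 60 = about minute 150.
- Counted from the start of the injection, the readings fall before 0, at 15 and at about 150.
- Counted from the end, the middle reading falls at 5 + 15 = minute 20.
- The first interval after dosing starts without a scheduled reading is therefore 15 or 20 minutes long.

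**Step 2. When a flush that starts during the injection would end**
- Earliest: onset at 0 plus 2 minutes = minute 2.
- Latest: onset at 5 plus 10 minutes = minute 15.
- If the reading is at minute 15, every such flush ends at or before it. If the reading is at minute 20, every such flush ends at least 20 − 15 = 5 minutes before it.
- A flush that starts later could overlap the reading. Because onset is not given, the conclusion is that the reaction *could* be missed by the schedule, not that it would be.

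**Step 3. What one added reading does**
- Reading at minute 5 (end of injection): if the middle reading is at 15, the unread intervals are 0–5 and 5–15, so the longest is 10 minutes instead of 15. If it is at 20, they are 0–5 and 5–20, so the longest is 15 instead of 20.
- Reading at minute 10 (about 5 minutes after the injection): if the middle reading is at 15, they are 0–10 and 10–15, longest 10. If it is at 20, they are 0–10 and 10–20, longest 10.
- A fixed extra reading narrows the gap but can still miss a flush of 2 to 5 minutes. A reading triggered by the reaction does not depend on guessing its onset.

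**Step 4. What the existing safeguards supply**
- Section 5.3: visual watch for flushing or redness, with no times given.
- Section 3.3: physician available.
- Section 8.2: questioning, examination as appropriate, follow-up of the event.
- None of these names a heart-rate or blood-pressure reading at the time of a reaction, and none rules one out.

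**Step 5. Cost**
- Scheduled readings: 20 subjects × 1 = 20, plus one per reaction.

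**The case against.** The strongest reply is that this is a preference, not a defect. Every intermittent schedule leaves intervals without a reading. Two sections state the same three times, which suggests a deliberate choice. No standard in the protocol is broken, no haemodynamic effect is reported and no haemodynamic endpoint exists. Staff are present, a physician is at hand, and nothing stops them from taking a pulse or pressure if they see a reaction. The full breast cancer report, attached to the protocol but not available here, may give the onset and perhaps readings taken during the flushing.

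Much of this stands. It limits the gain to the concurrent numeric reading and makes the point a cheap improvement. It does not remove the point, because a reading that staff may take is not one the plan asks for.

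A reader might infer more than the text supports:
- *That a reaction would go unnoticed.* Sections 3.3, 5.3 and 8.2 provide for observation, questioning and recording.
- *That a pressure change has been or will be missed.* No such effect is reported, so there is nothing from which to estimate one.
- *That about 3 of these 20 men will flush.* The 3 of 19 comes from women with breast cancer. Section 1.8 also describes 25 men imaged with the agent before prostatectomy but gives no adverse-event data for them.
- *That chart 15.1 drops the 15-minute reading.* The chart places vital signs before and after imaging. Imaging starts at 90 minutes, so a 15-minute reading is itself before imaging, and section 6.1 defers to the earlier schedule. The chart is less specific than 5.2 and 5.3 but does not conflict with them.

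**Conclusion.** The point holds as a minor design improvement. As scheduled, a brief reaction in the first 15 minutes after dosing starts (20 if timed from the end of the injection) can begin and end with no heart-rate or blood-pressure reading, and the only reaction reported with the agent is brief. The timing result rests on an assumed duration of 2 to 10 minutes and on onset during the injection, which the documents do not state. No share of reactions missed can be given, because onset is unknown. The effect is confined to the detail of the safety record. Subject numbers, the primary accuracy estimate and its confidence interval are untouched.

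**What to change.** In sections 5.2 and 5.3, add:
1. one reading of heart rate, respiratory rate and blood pressure at the end of the injection or about 5 minutes after it; and
2. one reading whenever flushing or any other reaction is seen by staff or reported by the subject. The trigger should include reported symptoms because sections 1.8 and 3.3 describe flushing that subjects felt and do not say it was visible.

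The second item matters more. The first is a fallback for a reaction that nobody notices or mentions at the time.

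The cost is a wording amendment to two sections, 20 short scheduled readings across the study, and one more for each reaction, by staff already present. No visit or staff member is added. Putting the clock times into visit chart 15.1 in the same amendment would help the coordinator, but is editorial only.
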